8.3.4 Exploratory Analysis

Agreement between a secondary endpoint (PVR calculated by site-based standards) and the standardized Fick-based calculation of PVR (PVR_f) will be assessed using the method of Bland and Altman, separately for baseline and Week 24 right heart catheterization. Analyses will also be subset on method of calculation of cardiac output (thermodilution vs. Fick) if found to be a significant predictor in the ANCOVA model.

This secondary efficacy analysis will be repeated for PVR_f. Change from baseline in the standardized Fick-based calculation of pulmonary artery capacitance (PAC_f) will also be analyzed in the same manner as the PVR efficacy analysis.

Additionally, the relationship between change in PVR and change in 6MWD at Week 24 will be analyzed using a Spearman's rank correlation coefficient. Relationships between additional clinical outcomes and 6MWD or PVR can also be provided. These clinical outcomes will be addressed in the SAP.

The analyses of Treatment Satisfaction responses will also be considered exploratory. Questions will include:

1. Do you think you benefited by being in the study?
2. Have you noticed any long term benefits from study treatment?
3. Do you think you received rituximab or placebo?

All exploratory analyses will be conducted on subjects in the ITT population with available data.

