2.3 Exploratory Objectives

- To evaluate agreement between PVR calculated by site-based standards and a standardized Fick-based calculation of PVR.

- To assess sensitivity of the secondary efficacy analysis to standardization of the PVR calculation.
- To assess the utility of a standardized derived pulmonary artery capacitance as a primary efficacy endpoint.
- To evaluate the relationship between 6MWD, PVR, and other clinical measures.

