8.3.2.2 Secondary Efficacy Analysis

All secondary analyses will be conducted in an exploratory fashion with p-values and confidence intervals presented as descriptive statistics with no adjustments for multiple comparisons. Tests will be two-sided and interval estimates will be generated at the 95% confidence level. As part of secondary analyses, appropriate contrasts will be constructed using model-based approaches. Larger models will be constructed for these comparisons with consideration of additional covariates that are found to differ between the treatment groups. Covariates may include, but are not limited to: study center, method of cardiac output, gender, disease duration and severity, and concomitant therapy use. All analyses will be repeated using the Per Protocol Population.

Change from baseline in PVR at Week 24 and percent change from baseline in PVR at Week 24 will be analyzed using an analysis of covariance, adjusting for treatment, method of cardiac output, and baseline PVR.

For the outcome time to clinical worsening, the two groups will be compared using survival approaches. Graphical summaries of time to clinical worsening will be generated using Kaplan-Meier survival curves with a log-rank test used to test for differences in the two arms. The two arms will also be compared after control of appropriate covariates using a Cox proportional hazards model.

For the proportion of subjects who changed or added PAH therapeutic agents, the treatment two arms will be compared using a logistic regression model, controlling for appropriate covariates. This will be done at the following time points: prior to week 24 and after week 24.

Longitudinal changes in continuous outcome measures including the subscales of the SF-36, the SHAQ, and DLCO will be compared across the two arms using linear mixed models. Initially the models will be used to describe changes between baseline and 24 weeks and

baseline and 48 weeks including only treatment, baseline levels of the outcome of interest, and an indicator if the measurement was affected by changed or new PAH therapeutic agents, with added models developed to assess the effect of other covariates.

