7.3.1. Pulmonary Vascular Resistance

Endpoint: A right heart catheterization (RHC) will be performed at Screening and Week 24. Data for the RHC will be collected on the Right Heart Catheterization CRF page.

During a RHC a catheter is guided to the right side of the heart and then into the pulmonary artery; blood flow through the heart is observed and is used to measure pressures in a subject's heart and lungs. Pulmonary vascular resistance (PVR) will be collected in Wood Units and method of cardiac output (indirect or estimated Fick, direct Fick, or thermodilution) will be collected as well. Multiple types of PVR (indirect or estimated Fick, direct Fick, or thermodilution) may be collected for a subject. Higher PVR values indicate worse disease status.

PVR will be derived in two ways:

1. First, as noted previously, multiple types of PVR (indirect Fick, direct Fick, or thermodilution) may be collected for a subject. The PVR value used for analysis will be chosen in the following order, as available from the Right Heart Catheterization CRF page: 1. thermodilution, 2. direct Fick, 3. indirect Fick. Both the screening and Week 24 RHC must use the same method of cardiac output. If the method used for screening and Week 24 do not match, only the baseline measure will be included in model-based analyses.
2. Second, PVR will be derived using the formula:

$$PVR = (mPAP - PCWP)/CO, \text{ where}$$

mPAP = mean pulmonary artery pressure (mmHg)

PCWP = mean pulmonary capillary wedge pressure (mmHg)

CO = Cardiac Output (L/min)

Similar to the first method, method of cardiac output will be chosen in the following order, as available: 1. thermodilution, 2. direct Fick, 3. indirect Fick. PCWP can be recorded at end expiration or by a computer-generated mean. If both are recorded, at end expiration will be used.

For each derived PVR variable, change from Screening to Week 24 in the PVR and percent change from Screening to Week 24 in the PVR will be computed for each subject. Missing values will not be imputed.

Analysis: For each derived PVR variable, the following analyses are planned.

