1. Descriptive statistics will be presented for PVR, percent change from Screening, and change from Screening in PVR for each treatment group and overall. Spaghetti plots and summary statistics including 25th percentile, mean, median, and 75th percentile will be plotted for each visit by treatment group. Separate summaries will be prepared for all subjects with available data at either time point and for the subset of subjects with measurements at both time points.
2. Additionally, a repeated measures mixed model will be fit with PVR as the outcome and treatment, visit week (actual observed week), and their interaction as predictors. Random intercepts and slopes will be fit for each subject using an unstructured covariance structure for each treatment group. Model estimates and standard errors for PVR and change from baseline in PVR will be presented at baseline and Week 24, along with the differences between arms. An appropriate contrast will be used to test the difference (baseline to Week 24) between treatment arms.

A separate analysis is planned to simultaneously evaluate the all reported PVR (indirect Fick, direct Fick, or thermodilution) measures for a subject without the prioritization rules described above. A multivariable repeated measures mixed model will be fit with PVR as the outcome and treatment, type of PVR (indirect or estimated Fick, direct Fick, or thermodilution), visit week (actual observed week) and interaction terms for type*treatment and type*treatment*week. Random intercepts and slopes will be fit for each subject using an unstructured covariance structure for each PVR type and treatment group. In addition, separate residual variance components will be estimated for each type of PVR.

Note: PVR is measured only at screening and Week 24. Subjects lost prior to Week 24 will contribute only screening data. If subjects are not lost completely at random, findings from these analyses may be biased as they will reflect changes in PVR in the subset of individuals who made it to Week 24.

Analogous analyses will be repeated on the percent change from Screening in PVR at Week 24.

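### The exploratory agreement analysis of site PVR against Fick-based PVR is split by cardiac-output method only on a significance test that addresses the wrong quantity and that the SAP's PVR model no longer supplies

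*Protocol*

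**What the plan says.** The first exploratory objective (Protocol 2.3) is "To evaluate agreement between PVR calculated by site-based standards and a standardized Fick-based calculation of PVR". Under Protocol 8.3.4, agreement "will be assessed using the method of Bland and Altman, separately for baseline and Week 24 right heart catheterization". The same paragraph adds a further, conditional step: "subset on method of calculation of cardiac output (thermodilution vs. Fick) if found to be a significant predictor in the ANCOVA model". The unsplit analysis is therefore the default and the split is conditional.

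The ANCOVA meant can only be the one in Protocol 8.3.2.2, where change and percent change in PVR at Week 24 "will be analyzed using an analysis of covariance, adjusting for treatment, method of cardiac output, and baseline PVR". The RESTORE sub-study also uses an ANCOVA, but with treatment, center and baseline value only.

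In SAP 7.3.1 the PVR analysis is different: "a repeated measures mixed model will be fit with PVR as the outcome and treatment, visit week (actual observed week), and their interaction as predictors". The site value is picked by a priority order: "1. thermodilution, 2. direct Fick, 3. indirect Fick. Both the screening and Week 24 RHC must use the same method of cardiac output". A separate model takes all reported PVR types together, with type as a term and "interaction terms for type*treatment and type*treatment*week", and a residual variance for each type. Nothing connects that model to the agreement analysis.

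The SAP as supplied repeats the agreement objective in its synopsis. Its body has no Bland-Altman section, and section 9 (Other Analyses) covers medications only.

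**The concern.** Whether two ways of obtaining PVR agree depends on how the cardiac output in the site value was obtained. Appendix E defines both site PVR and PVRf as the transpulmonary gradient over cardiac output, and PVRf takes its output from an assumed oxygen consumption, which makes it an estimated-Fick value. A site value from estimated Fick shares most of those inputs. A site value from thermodilution does not. The SAP recognises the mixture: "Multiple types of PVR (indirect or estimated Fick, direct Fick, or thermodilution) may be collected for a subject".

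The plan reports limits by method only if a different model, for a different outcome, gives a significant method term. If the differences do vary by method and the split is not made, the single set of limits describes a mixture. It could then suggest that site PVR is more interchangeable with PVRf than it is at thermodilution sites, and less so at estimated-Fick sites.

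**Working it through.** The documents give no bias, SD of differences, limits, method mix or significance level for this rule, so there is no planned figure to reproduce. The check compares the texts and then illustrates the size under stated assumptions.

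**1. Is the trigger supplied by a planned model?**
- Protocol 8.3.2.2: ANCOVA of change in PVR on treatment, method and baseline PVR. It has a method term.
- SAP 7.3.1, model for the chosen PVR value: treatment, week and their interaction. No method term.
- SAP 7.3.1, model for all types: has PVR type, but is not an ANCOVA and is not tied to the agreement analysis.
- SAP section 11: lists changes to 7.2.2, 7.3.3 and 7.3.4 only, although Protocol 8.5.6 says major departures will be noted in the SAP.

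**2. Would the ANCOVA, if fitted, detect the relevant difference?**
The Protocol (Week 24 visit; Table 6.1, note 20) and SAP 7.3.1 call for the same cardiac-output method at both catheterizations. Write site PVR as true value + offset for method + error. An offset common to both visits drops out of the change score. Adjusting for baseline puts back only a small part.

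Simulated check (3,000 trials per setting): 48 subjects (60 less 20% dropout); 60% on one method; true PVR mean 553 dyne-s/cm5 (Protocol 8.1). Assumed: SD of true PVR 250, error SD 100 at baseline and 330 at Week 24.
- The part of the offset that survives baseline adjustment is 100² / (250² + 100²) = 0.138, so an offset of 80 or 160 dyne-s/cm5 leaves 11 or 22 in the method coefficient.
- The method term was significant at 0.05 in 5.2%, 5.0% and 5.0% of trials for offsets of 0, 80 and 160. That is the false-positive rate.

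If method did affect change itself, the test would still rarely be significant. With the Protocol's SD of change of 350 dyne-s/cm5, 48 completers and an even mix, SE = 350 × √(2/24) = 101. The chance of significance in the true direction is Φ(Δ/SE − 1.96).

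| Effect of method on change, Δ (dyne-s/cm5) | 50:50 mix | 80:20 mix |
|---|---|---|
| 40 | 6% | 5% |
| 80 | 12% | 9% |
| 160 | 35% | 24% |

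**3. What do pooled limits then show?**
For share p on thermodilution, biases b_T and b_F, and SDs s_T and s_F:
- pooled mean = p·b_T + (1−p)·b_F
- pooled variance = p·s_T² + (1−p)·s_F² + p(1−p)(b_T − b_F)²
- limits = mean ± 1.96 × pooled SD
- coverage within a method = Φ((upper − b)/s) − Φ((lower − b)/s)

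With p = 0.5 (all biases and SDs assumed, in WU):

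| Bias T, F | SD T, F | Pooled limits | Own limits, thermodilution | Own limits, Fick | Coverage T, F |
|---|---|---|---|---|---|
| 0, 0 | 1.0, 1.0 | ±1.96 | ±1.96 | ±1.96 | 95%, 95% |
| 0, 0 | 1.0, 0.75 | ±1.73 | ±1.96 | ±1.47 | 92%, 98% |
| 0, 0 | 1.5, 0.5 | ±2.19 | ±2.94 | ±0.98 | 86%, about 100% |
| 1, 0 | 1.0, 1.0 | −1.69 to 2.69 | −0.96 to 2.96 | −1.96 to 1.96 | 95%, 95% |

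Third row: variance = 0.5 × 2.25 + 0.5 × 0.25 = 1.25, SD 1.118, limits ±2.19. In the last row coverage holds, but the pooled bias of 0.5 is the bias of neither method.

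**The case against.** The strongest reply has four parts.

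- **The trigger may still operate.** The ANCOVA remains in Protocol 8.3.2.2, and SAP section 11 does not withdraw it. This stands. A reader might infer that the split can never be made, but the two texts conflict and an analyst could still fit the Protocol model. What can be said is that no model in the SAP supplies the trigger, and that the Protocol model would be a poor one.
- **The SAP does not ignore method.** Its all-types model has PVR type as a term, type interactions and separate residual variances, with no significance condition. This also stands. That model compares types with one another and by treatment, however; it does not compare any of them with PVRf.
- **Harm from pooling is assumed.** A reader might infer that pooled limits are wrong for both methods. That holds only if bias or SD differs by method. The argument from shared inputs applies to estimated Fick; direct Fick is a separate method, and the documents do not say which oxygen-consumption formula sites use.
- **Little depends on it.** A reader might infer that the repeat of the PVR analysis on PVRf relies on these limits. It does not: Protocol 2.3 lists agreement and sensitivity as separate objectives, and the repeat takes no input from the Bland-Altman results.

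**Conclusion.** The rule for splitting the agreement analysis should go. It tests change in PVR where the question is the difference between site PVR and PVRf at each visit, and in the illustrative simulation it responded to a constant method offset no more often than chance. The SAP's PVR model has no method term, the replacement is undeclared, and the agreement analysis is not specified in the SAP as supplied. Pooled limits are therefore the default.

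How much that matters is unknown. Under the assumptions above, with an even mix, coverage of pooled limits within thermodilution runs from 95% (no difference between methods) to 86% (SDs of 1.5 and 0.5 WU). Some difference is plausible because PVRf is an estimated-Fick value, but the documents give no figure, and they do not support saying that pooled limits must be wrong. The 5% level for the trigger is also an assumption.

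This is a minor point, worth making because the repair is cheap. It touches one exploratory objective; the primary 6MWD analysis and the treatment comparisons are unaffected.

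**What to change.** 1. Delete the significance condition in Protocol 8.3.4.
2. At each visit, always report bias and limits of agreement by cardiac-output method beside the pooled result: thermodilution and Fick, with direct and indirect Fick separated where numbers allow. A fixed three-way split as the main result is not advisable with about 48 to 60 subjects and an unknown method mix.
3. Specify this agreement analysis in the SAP.
4. List the replaced PVR ANCOVA in SAP section 11.

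The cost is a few sentences, some extra plots and some precision. The approximate 95% confidence half-width of a limit is 1.96 × √(3/n) × SD: 0.69 SD with 24 subjects per method at Week 24 (even split assumed), against 0.49 SD with 48 pooled. Keeping the pooled result alongside means nothing already planned is lost.

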8.4 Interim Analysis

Results of interim analyses will be reported to the DSMB for planned Data Review Meetings. Reports prepared for these meetings will focus on study conduct and subject safety and may include information on enrollment, randomization, site activation status, protocol deviations, subject status and demographics, and safety analyses.

8.4.1 Interim Analysis of Efficacy Data

There will not be any interim analysis on efficacy data for this trial.

8.4.2 Interim Analysis of Safety Data

The DSMB will periodically review safety data as described in Section 7.8.2, *DSMB Review*. The safety analyses for this trial will be descriptive rather than inferential. Detailed listings and summary tabulations of adverse events and safety-related laboratory values will be generated as specified in the Statistical Analysis Plan. The safety analyses will be completed using the safety population without stratification.

No formal stopping rules for safety endpoints are specified.

8.5 Other Statistical Considerations

8.5.1 Covariates

The primary analysis will be adjusted for as stated above.

If the analyses described in Section 8.5.4, *Examination of Subgroups* yield covariates that differ significantly between treatment groups, then, as a secondary analysis, these covariates may also be considered for adjustment in the models specified for the primary analysis.

Covariates that may be considered include, but are not limited to: age, study center, gender, race, duration of SSc-PAH disease, baseline and concomitant medication use, undergoing cardiopulmonary rehabilitation (yes/no), non-biologic immunosuppressive or immunomodulating drug use (yes/no), and non-biologic immunosuppressive or immunomodulating drug change after 6 months (yes/no).

8.5.2 Multi-center Studies

Due to the small sample size and large number of sites needed for this study, study center will not be included as a covariate in the analysis. However, if evidence of a study center effect exists and there are appropriate sample sizes at each site, a sensitivity analysis will be performed including study center in the efficacy analyses. All safety analyses will be based on data pooled across all centers with no adjustment or stratification by center.

8.5.3 Multiple Comparisons and Multiplicity

This study has a single primary analysis designed to assess the efficacy of rituximab in clinical response as measured by change in PVR. Consequently, no adjustments for multiplicity are needed for Type I error protection. The secondary efficacy analyses are considered to be descriptive with p-values and confidence intervals presented as descriptive measures of strength of evidence rather than formal statistical inference. Therefore, no multiplicity adjustments are needed for this study.

8.5.4 Examination of Subgroups

Secondary analyses of the primary and secondary objectives may be conducted for the following subgroups:

- Race
- Ethnicity
- Gender
- Baseline PVR
- Baseline 6MWD
- NYHA Functional Class
- Duration of SSc-PAH disease

Additionally, exploratory analyses of responder subgroups and subgroups defined through the mechanistic and immunological studies will be conducted.

8.5.5 Missing Data

Standard procedures will be used to ensure that data are as complete and accurate as possible. In analyses, a full accounting will be made for all data items. Because this is a Phase II trial that is underpowered, there will not be any additional handling of missing data for the primary analysis. However, sensitivity analyses will be performed to assess the robustness of the conclusions under different assumptions. For example, missing data due to death of a subject prior to Week 24 would be handled differently than missing data due to a missed visit.

As described in Section 3.3.3.1, *Follow-up Requirements for All Treated Subjects*, every effort will be made to obtain 6MWD for patients withdrawing prior to the 24 week visit. For the primary analysis, this observation will be included in the repeated measures model and will contribute to the estimated mean change from baseline at Week 24.

Secondary analyses will be performed on all available data; no imputation will be performed on missing data, recognizing that these exploratory analyses could be biased in an unknown direction by non-ignorably missing data.

If data are missing for the primary endpoint, sensitivity analyses will be conducted to assess whether conclusions are robust to alternative analytic approaches for handling these data. If data are missing for other key endpoints, sensitivity analyses could also be conducted, if deemed appropriate. Details of the sensitivity analyses will be provided in the Statistical Analysis Plan.

8.5.6 Changes to the Statistical Analysis Plan

A detailed description of the planned analyses will be provided in a SAP to be completed and signed off prior to the completion of the trial. Major changes from this protocol will be noted in the SAP. If there is sufficient reason to do so, revised plans may be issued during the course of the study. Changes to the SAP that are made subsequent to database lock will be documented in the clinical study report.

9 ACCESS TO SOURCE DATA AND DOCUMENTS

Each participating site will maintain the highest degree of confidentiality permitted for the clinical and research information obtained from subjects participating in this clinical trial. Medical and research records should be maintained at each site in the strictest confidence. However, as a part of the quality assurance and legal responsibilities of an investigation, each site must permit authorized representatives of the IND sponsor, the SACCC, Genentech, Inc., and health authorities to examine (and when required by applicable law, to copy) clinical records for the purposes of quality assurance reviews, audits, and evaluation of the study safety and progress. Unless required by the laws permitting copying of records, only the coded identity associated with documents or other subject data may be copied (obscuring any personally identifying information). Authorized representatives as noted above are bound to maintain the strict confidentiality of medical and research information that may be linked to identified individuals. Participating sites will normally be notified in advance of auditing visits.

All subject records and study documentation will be kept after the protocol is completed. This will include all documentation of AEs, records of study drug receipt and dispensation, and all IRB correspondence. All study records will be kept for at least 2 years after the investigation is completed.

